5.3. Key Dates Time Period Definitions

The following time periods will be defined for efficacy and safety analyses:

205MS301 Treatment Period

The 205MS301 Treatment Period is the time period as defined in the 205MS301 statistical analysis plan and includes data collected from the first dosing date to the end of treatment period visit in the 205MS301 study. For subjects who completed study treatment this is the date of the last scheduled treatment period visit in that study.

205MS303 Treatment Period refers to the time between the first dose date in 205MS303 and the date of the last available measurement prior to 180 days after the last dose date in 205MS303. This is the time period for most of the efficacy analyses and for all the safety analyses for all the populations.

Combined Study Period

For the 205MS301-303 ITT population, the Combined Study Period is the combined period of the 205MS301 and 205MS303 studies, that is the time between the first dose date in 205MS301 and the date of the last available measurement prior to 180 days after last dose date in 205MS303.

Note that for the 205MS203-303 ITT population and the 205MS302-303 ITT population, the combined study period is not necessary due to the limited number of patients in each population.

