1.2. Secondary Objective and Endpoints

Secondary objectives of this study in this study population are as follows:

- To describe MS-related outcomes, including MS relapse, disability progression, MS lesion formation, and patient-reported impact of MS, following long-term treatment with DAC HYP
- To assess the long-term immunogenicity of DAC HYP administered by prefilled syringe (PFS)
- To assess the safety, tolerability, and efficacy of switching to DAC HYP in subjects previously on long-term treatment with interferon β -1a (IFN β -1a) in Study 205MS301

The secondary endpoints of this study are as follows:

- Relapse outcomes: annualized relapse rate (ARR), and proportion of subjects who relapse
- Sustained disability progression defined by at least a 1.0-point increase on the Expanded Disability Status Scale (EDSS) score from a baseline EDSS ≥ 1.0 that is sustained for 24 weeks, or at least a 1.5-point increase on the EDSS from a baseline EDSS < 1.0 that is sustained for 24 weeks
- Magnetic Resonance Imaging (MRI) outcomes: total number and volume of new or newly enlarging T2 hyperintense lesions, Gd-enhancing lesions, T1 hypointense lesions, and brain volume change on brain MRI
- Change in Multiple Sclerosis Functional Composite (MSFC) score
- Change in EDSS score
- Change in Symbol Digit Modalities Test (SDMT) score
- Change in 3 Second Paced Auditory Serial Addition Test (PASAT 3) score
- Proportion of subjects who are free from disease activity.

[figure not shown]
- Change in Multiple Sclerosis Impact Scale-29 (MSIS-29) physical and psychological scores
- Change in quality of life as assessed by the European Quality of Life, 5 dimensions and European Quality of Life, Visual Analogue Scale (EQ-5D and EQ-VAS)
- Change in direct health resource utilization (HRU; hospitalizations, emergency room visits, and unscheduled neurologist visits)
- Change in treatment satisfaction as assessed by the subject
- Change in subject productivity as assessed by the Health Related Productivity Questionnaire (HRPQ)
- Changes in clinical laboratory assessments (hematology and blood chemistry)
- Local tolerability as assessed by subject-reported injection site pain, Visual Analogue Scale (VAS) and clinician injection site assessments
- Incidence of anti-drug antibodies (ADAs) to DAC HYP over time
- Incidence of neutralizing antibodies (NAbs) to DAC HYP over time

2. Study Design

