7.1. Summary of Efficacy Analyses

Table 7 shows the overall summary of the efficacy analyses.

For the 205MS301-303 ITT population, efficacy analyses will be performed in the 205MS303 Treatment Period and the Combined Study Period. Selected analyses will be also done for the 205MS301-303 ITT population in the 205MS301 Treatment Period for evaluation with corresponding results in the 205MS303 Treatment period (e.g., for the annualized relapse rate). For the combined study period, data from the last dose of study treatment in 205MS301 to the first dose of study treatment in 205MS303 will also be included in the analysis.

For the 205MS203-303 ITT population, efficacy analyses will be performed in the 205MS303 Treatment Period, and will be summarized for all subjects combined. For the 205MS302-303 ITT population, efficacy analyses will be performed in the 205MS303 Treatment Period. Note that for subjects in the 205MS203-303 ITT population and the 205MS302-303 ITT population, due to the inherent difference in dosing and treatment in their previous studies, efficacy analyses will only be performed in the 205MS303 Treatment Period.

Table 7: Summary of populations and treatment periods for efficacy analyses

Population	Study/Treatment Period	Baseline
205MS301-303 ITT population	205MS301 Treatment Period	205MS301 Baseline
	205MS303 Treatment Period	205MS303 Baseline
	Combined Study Period	205MS301 Baseline
205MS203-303 ITT population	205MS303 Treatment Period	205MS303 Baseline
205MS302-303 ITT population	205MS303 Treatment Period	205MS303 Baseline

	Protocol 205MS303 Statistical Analysis Plan	Final Version 1.0
---	--	--------------------------

The following three tables include endpoints, analysis populations, baseline type with a short summary of statistical methods for the efficacy analyses. Sections below include more details about these analyses.

Table 8: Summary of efficacy analyzes for the 205MS301-303 ITT population

Endpoint	Population	Study/Treatment Period	Baseline	Statistical Methods
Annualized relapse rate	205MS301-303 ITT population	Combined Study Period	205MS301 Baseline	Unadjusted and adjusted ARR. Adjusted ARR will be estimated from the negative binomial model, adjusting for age, prior IFN beta, baseline EDSS and baseline relapse rate at the 205MS301 Baseline.
		205MS301 Treatment Period	205MS301 Baseline	As above

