The relapse rate will be reported using relapses that occurred on or after the first dose date during the applicable study period. Relapses that occur after subjects receive alternative MS medications will be excluded from the analyses of relapse rate, and the subject's time on study will be censored at the time the alternative MS medication is added. For each analysis period, the subject's time on study will be censored at the time the alternative MS medication in the given period. For example, if a subject from the 205MS301-303 ITT population took alternative medication in the 205MS301 study before the first dose in study 205MS303 and in the 205MS303 study, this subject will be included in the analyses of the 205MS303 Treatment period and will be censored at the time the alternative MS medication in the 205MS303 study.

The unadjusted ARR will be calculated as the total number of relapses experienced during the given period, divided by the total number of days in the study period or the time of censoring, and the ratio then multiplied by 365.25. Relapse rate may be tabulated by the 205MS301 study treatment group (IFN β -1a 30 μ g and 150 mg DAC HYP).

	Protocol 205MS303 Statistical Analysis Plan	Final Version 1.0
---	--	--------------------------

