7.2.2. Annualized Relapse Rate in the 205MS203-303 ITT Population

The annualized relapse rate will be summarized for the 205MS203-303 ITT population in the 205MS303 Treatment period. The relapse rate will be reported using relapses that occurred on or after the first DAC HYP dose date in the 205MS303 Treatment period. Relapses that occur after subjects receive alternative MS medications will be excluded from the analyses of relapse rate, and the subject’s time on study will be censored at the time the alternative MS medication is added.

The unadjusted ARR will be calculated as the total number of relapses experienced during the given period, divided by the total number of days in the period or the time of censoring, and the ratio then multiplied by 365.25. Relapse rate will be tabulated for all subjects combined.

For the 205MS303 Treatment period, the relapse rate will also be estimated using a negative binomial model, with adjustment for the number of relapses in a year prior to the first dose in 205MS303. The logarithmic transformation of the number of days in the study will be included in the model as the “offset” parameter. If the data are under-dispersed (assessed using the Pearson Chi-Squared statistic) or if the negative binomial model does not converge, a Poisson regression model will be used instead. The Poisson model will be adjusted for over-dispersion using a Pearson scale parameter.

To further assess the durability of treatment, the relapse rate will also be summarized by 48-week time intervals defined in the 205MS303 Treatment Period. For these analyses, rates will be tabulated by evaluating the number of relapses in each time interval and the amount of follow-up time in the time interval. A Poisson model will be used to estimate the relapse rate in each time interval unless data are over-dispersed in which case a negative binomial model will be used.

	Protocol 205MS303 Statistical Analysis Plan	Final Version 1.0
---	--	--------------------------

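### The 205MS303 relapse analyses run up to 180 days past the last dose while the 205MS301 period stops at end of treatment, so the switch and durability ARRs include post-dosing time

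*SAP*

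**What the plan says.** SAP section 5.3 gives the two treatment periods different ends. The 205MS301 period "includes data collected from the first dosing date to the end of treatment period visit in the 205MS301 study". The 205MS303 period starts at the first 303 dose and ends at "the date of the last available measurement prior to 180 days after the last dose date in 205MS303". Of the 303 period the section adds: "This is the time period for most of the efficacy analyses and for all the safety analyses for all the populations".

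These periods feed the relapse analyses. Section 7.1 plans selected 301 results "for evaluation with corresponding results in the 205MS303 Treatment period" and names the ARR as its example. Section 1.2 lists the matching secondary objective: "To assess the safety, tolerability, and efficacy of switching to DAC HYP in subjects previously on long-term treatment with interferon" (beta-1a).

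In section 7.2.1 the unadjusted ARR is the relapse count "divided by the total number of days in the study period or the time of censoring, and the ratio then multiplied by 365.25". The adjusted model uses log days in the study as its offset. The only censoring event is the start of alternative MS medication; the end of DAC HYP dosing does not censor. Sections 7.2.1 to 7.2.3 also plan or allow the ARR by year (301 cohort) or by 48 weeks (203 and 302 cohorts). For the 203 cohort: "To further assess the durability of treatment, the relapse rate will also be summarized by 48-week time intervals defined in the 205MS303 Treatment Period". Time to first relapse (section 7.3) uses the same period end. No on-treatment version of any of these is specified.

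Table 5 makes post-treatment follow-up mandatory, with the final visit 24 weeks after the last dose. Section 2 notes that the sponsor closed the study early and ended dosing by 30 March 2018.

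**The concern.** A relapse four months after the last 303 dose enters the 303 ARR. A relapse equally long after the last 301 dose falls outside the 301 Treatment Period. The two rates are then read together to judge the switch from IFN beta-1a.

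If relapses are more frequent once the drug is stopped, the 303 rate rises, the benefit of switching looks smaller than it was on drug, and late intervals look worse. Because the interval rates are labelled as evidence on durability, that rise could be read as waning effect.

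The post-dosing time is not confined to early dropouts. Follow-up is required of everyone, and the final visit (day 168 ± 10, so days 158 to 178) lies inside the 180-day limit. Section 8.2 uses the same 180 days for adverse events, where it fits. The SAP gives no reason for using it for relapse rates.

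**Working it through.** The plan states no relapse rate, sample size or power on this point, so there is no figure to reproduce. The check is person-time arithmetic.

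**Inputs**
- Dosing every 4 weeks (section 2).
- The 203 and 302 cohorts enter at Week 144 (Table 3).
- End of Treatment is Week 240, 4 weeks after the last dose (Table 4), so the last planned dose is at Week 236.
- The final visit is 24 weeks after the last dose (Table 5), so Week 260 on the full schedule.
- The ratio k of off-drug to on-drug relapse rate is not in the SAP. Assumed range: 1 to 3.

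**Step 1: time beyond the dosing interval.** 24 − 4 = 20 weeks per subject, at most.

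**Step 2: share of the period and effect on the ARR.** Share f = 20 / (weeks from first 303 dose to final visit). Whole-period ARR divided by on-drug ARR = (1 − f) + f·k, so inflation = f·(k − 1).

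| Subject | Period (weeks) | f | k = 1 | k = 2 | k = 3 |
|---|---|---|---|---|---|
| 203 or 302 cohort, full schedule | 260 − 144 = 116 | 20/116 = 17.2% | 0 | 17% | 34% |
| 301 cohort, full schedule | 260 | 20/260 = 7.7% | 0 | 8% | 15% |
| Last dose at Week 48 | 48 + 24 = 72 | 20/72 = 27.8% | 0 | 28% | 56% |

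These use nominal visit weeks. Stretching the tail to the 180-day limit leaves 180 − 28 = 152 days beyond the dosing interval. The shares become 152/(644 + 180) = 18.4%, 152/(1652 + 180) = 8.3% and 152/(336 + 180) = 29.5%, a difference of 0.6 to 1.7 points.

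**Step 3: the interval rates.**
- *203 and 302 cohorts.* Interval breaks fall 48 and 96 weeks after entry, and planned End of Treatment is 240 − 144 = 96 weeks after entry. For a subject who follows the full schedule, the third interval (weeks 96 to 116) is off drug.
- *301 cohort.* Section 7.2.1 says by year without defining a year. With the 48-week years of the schedule tables, Weeks 240 to 260 form a separate off-drug piece. With 365.25-day years, Year 5 starts at 4 × 365.25/7 = 208.7 weeks and ends at 260.9, so the off-drug share is 20/(260 − 208.7) = 39%.
- *Earlier stop.* The tail falls in an earlier interval. If all 152 days lie in one 336-day interval, they are 152/336 = 45.2% of that subject's time in it, and the inflation is 45% at k = 2 and 90% at k = 3.

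**Step 4: what this does to the switch contrast.** Assume a true on-drug 303/301 rate ratio of 0.50 and k = 2. With the 180-day shares, the reported ratio is 0.50 × 1.083 = 0.541 for a last dose at Week 236 and 0.50 × 1.295 = 0.647 for a last dose at Week 48. With k = 1 it stays at 0.50.

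**The case against.** The case for leaving the plan alone has three parts.

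First, the tail is often shorter than 20 weeks. Censoring at alternative MS medication acts most after dosing stops, because that is when another therapy would be started. The period also ends at the last available measurement, so a subject lost after End of Treatment adds little or nothing.

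Second, the SAP gives no post-dosing relapse rate and does not address residual drug effect beyond the dosing interval. At k = 1 there is no bias.

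Third, the consequence is limited. The primary endpoints are AEs and SAEs, section 5.4 calls the analyses generally descriptive, and the 301-to-303 contrast is an uncontrolled before-after comparison with no power resting on it.

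All three stand as limits on size. None removes the difference in period ends, and the censoring rule makes the remaining off-drug time selective, since it comes from subjects left without another therapy.

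A reader might infer more: that the last interval contains no treatment at all, that nearly every subject contributes the full tail, or that a late rise would show the effect of stopping. The SAP does not support these readings. The wholly off-drug interval holds only on a schedule that section 2 says was cut short and, for the 301 cohort, only if a year means 48 weeks. The full tail ignores the censoring rule. The cause of a late rise depends on a rate ratio that the document does not give.

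**Conclusion.** The point holds in a bounded form. The 301 and 303 treatment periods end by different rules, their ARRs are to be evaluated together, and nothing in the plan separates on-drug from post-dosing time on the 303 side. The shares of about 17%, 8% and 28% are maxima on the nominal schedule, and the inflation of 0 to at most 34%, 15% and 56% rests entirely on the assumed k of 1 to 3. Late intervals can be largely off drug, so a rise there could be misread as waning effect.

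The harm is to the interpretation of secondary, descriptive results. Type I error and the primary safety endpoints are not affected. The Combined Study Period closes by the same 180-day rule, so its relapse results need the same caution.

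**What to change.** For ARR, ARR by interval and time to first relapse:

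- Add an on-treatment analysis that ends 205MS303 person-time at the End of Treatment visit, or 28 days after the last dose if that visit is missing. Alternative MS medication still censors earlier.
- Use the matching number of days as the denominator and as the model offset.
- Base the 301-versus-303 comparison and the durability tables on this analysis, and state whether a year is 48 weeks or 365.25 days.
- Report relapses and person-time from that point to 180 days after the last dose as a separate post-treatment interval.
- Keep the 180-day window for safety and for confirming EDSS progression.

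The cost is one extra date derivation and somewhat less person-time in the on-treatment ARR. No data are lost, because the later relapses are still reported.

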5.4. General Methods of Analysis

For the 205MS301-303 ITT population, efficacy analyses will focus on data from the 205MS303 treatment period but will include some additional analyses across the combined study period. In general, summary statistics will be presented by previous treatment group of the 205MS301 study (IFN β -1a 30 μ g and 150 mg DAC HYP). Safety analyses will include subjects in the 205MS301-303 Safety Population and use the data from the 205MS303 Treatment period only. Analyses will be presented by previous treatment group of the 205MS301 study (IFN β -1a 30 μ g and 150 mg DAC HYP) and for all subjects combined.

For the 205MS203-303 ITT population, efficacy analyses will focus on data from the 205MS303 treatment period. Summary statistics will be summarized for all subjects combined. Safety analyses will include the data from the 205MS303 Treatment period, and will be presented for all subjects combined. Note that subjects enrolled from the 205MS203 study may receive DAC HYP at a higher dose (300 mg) during the 205MS201 and/or 205MS202 studies. Given the long duration time since last exposure to high dose of DAC HYP and to be consistent with the analyses in the 205MS203 clinical study report, analyses will not be presented by high/low dose level in previous studies.

For the 205MS302-303 ITT population, efficacy and safety analyses will focus on subject data from the 205MS303 treatment period, and will be presented for all subjects combined.

Analyses will generally be descriptive in nature. For relevant efficacy analyses, confidence intervals will be provided for each treatment group where appropriate to characterize the variability around the point estimates. Statistical hypothesis testing may be completed for selected analyses [REDACTED]

Visit Windows

For by-visit analyses, visit windows will be utilized. Data will be windowed to the nearest scheduled visit. If two or more evaluations occur in the same visit window, the evaluation measured on a day closest to the target visit day will be selected for inclusion in the analysis. If multiple evaluations are equally close to the target visit day, then the evaluation with an earliest day will be selected for inclusion in the analysis. If several samples are collected on the same day but at different times, the earliest time will be used.

Missing measurements

In general, no imputation for missing measurements will be performed, unless specified otherwise.

Missing dates

For start date of adverse events, if all available start date information is the same as that of the date of first dose in 205MS303, and the event did not end prior to first dose, the date of first dose in 205MS303 will be used as the imputed date. Otherwise for adverse events, and always for the start of concomitant medications, the earliest possible start date based on available partial information will be used. Namely, if only the day is missing, the 1st of the month will be used; if the month is also missing, January 1st will be used. End dates for concomitant medications and adverse events will not be imputed. For evaluations other than adverse events and concomitant medications, missing or incomplete dates that are needed for analysis will also be imputed. If the day is missing for a study procedure or assessment but the month and year are present, the day will be imputed as the 15th of the month. Month and year will not be imputed for study procedures or assessments. These same rules will be applied to missing or incomplete dates for relapses.

	Protocol 205MS303 Statistical Analysis Plan	Final Version 1.0
---	--	--------------------------

6. Study Subjects

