6.4. Concomitant Therapy

Medications (prescribed or over-the-counter) and non-drug therapies are considered concomitant if they are used during the study (i.e., either started prior to the study and continued while on study or started after the first dose of study treatment). Medications started more than 180 days after the last dose of study treatment are not considered concomitant. The World Health Organization (WHO) dictionary will be used for coding concomitant medication, and the Medical Dictionary for Regulatory Affairs (MedDRA) will be used for coding concomitant non-drug therapies.

The number and percentage of subjects taking any concomitant medications in 205MS303 will be reported for the 205MS301-303 safety population, the 205MS203-303 Safety Population, and the 205MS302-303 Safety Population, respectively. The most frequent concomitant medications, defined as those taken by at least 10% of subjects, and use of alternative MS medications and steroids may also be summarized.

The list of potential hepatotoxic medications is defined and agreed by SABR prior to data base lock. The number and percentage of subjects taking any potential hepatotoxic concomitant medications in 205MS303 will be reported for the 205MS301-303 safety population, the 205MS203-303 Safety Population, and the 205MS302-303 Safety Population, respectively.

7. Efficacy Data

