7.3. Proportion of Subjects who Relapsed

7.3.1. Proportion of Subjects with Relapse in the 205MS301-303 ITT Population

The proportion of subjects who relapsed will be summarized using the following study population and study periods

- 205MS301-303 ITT population in the combined study period
- 205MS301-303 ITT population in the 205MS303 Treatment period

Relapse will be defined using the same definition that was used for the annualized relapse rate endpoint. The proportion of subjects who relapsed at selected time points, by treatment group of the 205MS301 study, will be estimated.

Kaplan-Meier curve of time to the first relapse during the study period (i.e., the Kaplan-Meier product-limit estimator) will be used to estimate the proportion of subjects who relapsed. If there are no early withdrawals, the Kaplan-Meier estimate of the proportion of subjects relapsed is same as the observed proportion of subjects relapsed. If there are early withdrawals, the Kaplan-Meier estimate has the advantage of taking into account the length of follow-up for the early withdrawals, without having any assumptions about whether those subjects relapsed or not.

Subjects without a confirmed relapse will be censored at either early withdrawal or the end of the corresponding study period. If a subject took an alternative MS medication before the first relapse, the subject will be censored at the time of the alternative MS medication. Kaplan-Meier plots of the

	Protocol 205MS303 Statistical Analysis Plan	Final Version 1.0
---	--	--------------------------

time to first relapse will also be presented and used to estimate the median time (and/or the 25th percentile) by the previous treatment group of the 205MS301 study.

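### Partial start dates of alternative MS medication go to the earliest possible day, so a relapse that preceded the switch can be excluded as if it followed it

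*SAP*

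**What the plan says.** SAP section 5.4 (Missing dates) states for medications that "always for the start of concomitant medications, the earliest possible start date based on available partial information will be used". It then spells this out: "if only the day is missing, the 1st of the month will be used; if the month is also missing, January 1st will be used". Adverse events have a separate provision. When the available part of the start date matches the first 205MS303 dose and the event had not ended before it, the dose date is used. Medications have no such provision.

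For assessments with a missing day, "the day will be imputed as the 15th of the month", and the section adds that "These same rules will be applied to missing or incomplete dates for relapses". Read in place, that sentence refers to the assessment rule just before it.

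Section 6.4 treats alternative MS drugs within concomitant therapy ("use of alternative MS medications and steroids may also be summarized"), and the SAP gives no other date rule for them.

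Their start date then acts as a cut-off. Section 7.2.1 states "Relapses that occur after subjects receive alternative MS medications will be excluded from the analyses of relapse rate", and that the subject's "time on study will be censored at the time the alternative MS medication is added". Sections 7.2.2 and 7.2.3 repeat this for the other two cohorts. For time to first relapse, section 7.3.1 states "If a subject took an alternative MS medication before the first relapse, the subject will be censored at the time of the alternative MS medication", and sections 7.3.2 and 7.3.3 do the same.

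**The concern.** Taking the earliest date is a sensible default when the question is whether a drug was concomitant. It is not neutral when the same date decides whether a relapse counts. Suppose a subject relapses on 10 June and starts another MS drug on 24 June, recorded only as June. The drug is dated 1 June, the relapse appears to follow it, and the relapse leaves both the ARR and the time-to-first-relapse analysis. Nothing in the SAP lets the known order of events override the imputed date. If switches tend to follow relapses, the relapses lost are the ones that led to the switch.

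There is a second effect. A drug started on study, with only the year known, in the calendar year of the first 205MS303 dose is dated January 1st, which can precede that dose. Section 7.2.1 censors each period only for alternative medication in that period. In the 205MS303 Treatment Period this subject may therefore not be censored at all.

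**Working it through.** The SAP gives no figure on this point, so there is none to reproduce. The check applies its rules to every possible switch date.

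**Chance of losing a relapse.** Let the relapse start L days before the true switch, and let the switch fall on any day of three calendar years (1,096 days). Section 7.2.1 excludes relapses after the medication, so a relapse is lost if its onset is strictly later than the imputed start. For L up to about 27 days the day-missing result is close to (30.44 − L − 1)/30.44, where 30.44 is the mean month length. With only the year known it is (365.33 − L − 1)/365.33. Enumeration gives:

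| L (days) | Day missing | Only year known |
|---|---|---|
| 7 | 74% | 98% |
| 14 | 51% | 96% |
| 21 | 28% | 94% |
| 28 | 5% | 92% |
| 60 | 0% | 83% |
| 90 | 0% | 75% |

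Check at L = 14: (30.44 − 15)/30.44 = 0.507 and (365.33 − 15)/365.33 = 0.959.

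If relapse and switch fall in the same month and both lack the day, the relapse is dated the 15th and the drug the 1st. The relapse is then always excluded.

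**Direction.** The imputation removes on average 14.7 days of follow-up (day missing) or 182 days (only year known). At L = 14, assuming half of switches follow a relapse, the removed time carries:
- day missing: 0.5 × 0.507 / (14.7/365.25) = 6.3 relapses per person-year
- only year known: 0.5 × 0.959 / (182/365.25) = 0.96, about 1.0 per person-year

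Both exceed an assumed ARR of 0.15 to 0.30, so removing this time lowers the ARR. A record with no relapse in the unresolved interval loses only event-free time, which raises the ARR slightly. At an assumed ARR of 0.20, 14.7 days hold 0.20 × 14.7/365.25 = 0.008 expected relapses. The net effect of day-missing records is therefore downward once more than about 0.8% of them lose a relapse.

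**Size.** The cohort of about 1200 from 205MS301 is in SAP section 2. Every other input is assumed: 3 years each, L = 14, day missing.

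Central case (ARR 0.20, 10% switch, 10% of switch dates lack the day, 50% of switches follow a relapse):
- Person-years: 1200 × 3 = 3600. Relapses: 0.20 × 3600 = 720.
- Partial records: 1200 × 0.10 × 0.10 = 12. Relapses lost: 12 × 0.5 × 0.507 = 3.04.
- Time removed: 12 × 14.7/365.25 = 0.48 years, carrying a further 0.48 × 0.20 = 0.10 background relapses.
- ARR: (720 − 3.04 − 0.10)/(3600 − 0.48) = 0.1992, a fall of 0.4%.

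Range:
- Smallest effect (ARR 0.30, 5% switch, 5% partial, 50% following a relapse): 0.76 relapses lost, 0.3000 to 0.2998, a fall of 0.07%.
- Largest effect (ARR 0.15, 20% switch, 30% partial, all following a relapse): 36.5 relapses lost, 0.1500 to 0.1398, a fall of 6.8%.

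**The case against.** The strongest reply is that this will seldom matter. Concomitant therapy is recorded throughout the study, on-treatment clinic visits are at most 12 weeks apart, and the unscheduled relapse visit is due within 72 hours of symptoms. Unknown months and unknown relapse days should be rare. The SAP does not say how often dates are partial, or that switches follow relapses. The ARR is a secondary endpoint in a mainly descriptive analysis whose primary endpoints are adverse events and serious adverse events. All of this stands and limits the size of the point. It does not change what the rule does to a record with a partial date.

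A second reply is that moving every partial date to the latest possible day has its own bias. It would keep up to a month, or up to a year, on the new drug, which the SAP means to exclude. This also stands, and is why the fix below is narrower.

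Three stronger readings may tempt a reader, and the SAP does not support them:
- **The error favours the drug on every record.** It does not. Records with no relapse in the unresolved interval push the ARR up, and for day-missing dates a relapse 60 or more days before the switch is never lost. The uncensored year-only case is a separate error.
- **Freedom from disease activity is biased too.** Section 7.13 states no exclusion or censoring at alternative MS medication, so this cannot be read from the SAP.
- **Hepatotoxic drugs with partial dates generally fall in the section 8.6 category of first use before DAC HYP.** That can happen only when the partial date shares the month or year of the first DAC HYP dose. For subjects already on DAC HYP in an earlier study, that dose lies before 205MS303. The case concerns mainly former IFN β-1a subjects.

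**Conclusion.** The concern holds as a minor defect in a stated rule. Followed exactly, sections 5.4, 7.2 and 7.3 can reverse the order of a relapse and a later switch, and always do so when both lack the day in the same month. The lower ARR rests on the assumption that switches tend to follow relapses within weeks. With longer lags the loss from day-missing dates disappears and the small upward pull remains. The quoted range for the ARR rests on assumed switch rates, partial-date rates and a 14-day lag, and covers day-missing dates only. The missing floor at the first 205MS303 dose is a separate gap, and whether it affects any subject depends on year-only records whose number is not given.

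**What to change.** Add an exception to section 5.4 for alternative MS medications whose start date is used for censoring or exclusion:

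- **(a)** An imputed start may not precede a relapse that the record shows, or that the partial dates allow, came before the switch, unless the record shows that the drug came first. In the June example the drug would be dated no earlier than 10 June. With both days missing it would be dated no earlier than the 15th.
- **(b)** A drug recorded as started on study may not be dated before the first 205MS303 dose, mirroring the provision already made for adverse events.
- **(c)** Keep the present earliest-date rule as a sensitivity analysis for the ARR and time to first relapse, and report the number of partial dates affected.

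The cost is one paragraph of SAP text, a change to one date derivation and one extra run of the relapse analyses. Some relapses and time on the new drug may be retained, and the ARR may be slightly less favourable. The sensitivity analysis shows how much depends on the choice.
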